"We're calling to remind you that the follow-up telephone interview for the study, Effects of Effects of traumatic brain injury and post traumatic stress disorder on Alzheimer's disease (AD) in Veterans using ADNI, will begin in about 6 months from now, and to check in on how you are doing.

- Have you had any change in memory or thinking in the past 6 months?
 - Yes or no; If yes, specify:
- Have you had any overall change in activity in the past 6 months?
 - Yes or no; If yes, specify:
- Is there anything that you cannot do now, that you could do 6 months ago?
 - Yes or no; If yes, specify:
- Have you had any changes in medications, illness, surgeries or hospital visits in the last 6 months?
 - Yes or no; If yes, specify:

Thank you so much for your help. We'll be calling you in about 6 months to begin the follow-up interview.

- If at the 6 month reminder/check in call, the subject indicates that they do not want to continue the study in the next 6 months, we will ask them whether or not they would be willing to move their one year visit to the time of the 6 month call and make it an exit visit, and complete as many procedures as they are willing.
- 9. The follow-up screener, follow-up clinical telephone interview, and follow-up self administered questionnaires will be identical to the baseline questions, but will only reference the time period since the last baseline clinic visit. The follow-up screener will not be screening anyone out of the study, but will help us determine whether anything has changed since the last clinic visit that may make a particular procedure unsafe, and to determine that the subject is still willing and

able to participate.

- 10. Mild Cognitive Impairment/dementia at the time of the follow-up procedures will NOT be exclusionary, unless it would be unsafe for the subject to participate. With the exception of the lumbar puncture and the PET scan, all procedures at the clinic sites will be repeated at the follow-up visit unless there are specific health reasons that may make it unsafe for the subject to participate (for example, new metal implants).
- 11. Analysis of the data to test the hypotheses as stated, including the exploratory analyses, will begin after the first 12 months or so and will continue until the follow-ups are completed.
- 12. Deliver final report to the DOD.
- 13. Should additional funding be obtained, the number of longitudinal follow-up years may be increased.

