The primary hypothesis to be tested (all data analyses will be covaried for age, gender, and Apolipoprotein E (APOE) 4 genotype) are that Veterans without MCI/dementia with a history of moderate to severe TBI during military service, as well as Veterans with ongoing PTSD, have increased evidence for AD pathophysiological markers, when compared with Veteran controls (without TBI or PTSD and matched for age, APOE4 status and accounting for other comorbidities) manifested as the following dependent variables:

- Greater uptake on Florbetapir F18 amyloid PET scans;
- Lower CSF amyloid beta levels;
- Increased CSF tau/P tau levels;
- Greater brain atrophy in hippocampus, entorhinal cortex, and parietal/temporal cortices;
- Greater longitudinal rates of brain atrophy in hippocampus, entorhinal cortex and parietal/temporal cortices;
- Reduced cognitive function, especially delayed memory; and
- Greater rate of change of cognitive function.

Second Hypothesis

The second major hypothesis to be tested is that TBI and/or PTSD reduce brain reserve, causing greater cognitive impairment after accounting for age, educational status, and pre-war cognitive function as assessed with the Armed Forces Qualifying Exam score during basic training, brain amyloid load or hippocampal volume. Greater cognitive impairments at a given level of brain Aβ or brain volume in the TBI or PTSD group compared with controls would support the hypothesis of reduced cognitive reserve.

Third Hypothesis

The third hypothesis will be that TBI, when compared to controls, is associated with changes in brain regions previously reported to be associated with TBI [37-39]. White matter regions frequently noted to have reduced microstructural integrity due to TBI on DTI include the anterior corona radiata, uncinate fasciculus, corpus callosum, forceps minor, forceps major, sagittal stratum, corticospinal tract, inferior fronto-occipital fasciculus and cingulum bundle [37-39]. Previous findings of reduced hippocampal volume in PTSD compared to controls will also be replicated [32-36].

Fourth Hypothesis

The fourth hypothesis is that there will be significant correlations between severity of TBI (from hospital records) and severity of PTSD (CAPS score) on the above-listed outcomes, i.e. a dose response effect.

Exploratory Analyses

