Exploratory analyses will be performed to examine other questions; although, after correction for multiple comparisons, the statistical significance of these will be low, requiring future replication. Nevertheless, the patterns of amyloid deposition (from Florbetapir uptake) and brain atrophy between TBI, PTSD, and control subjects will be compared, with similar patterns from non-Veteran subjects in ADNI. These results of these studies may provide insight into the question of whether or not TBI and PTSD alter the pattern of amyloid distribution or brain atrophy. Such analyses may also give insight into the question of whether TBI or PTSD is associated with reduced cognitive reserve. The relationship between cortical areas with amyloid plaque (from amyloid PET) and underlying white matter integrity as assessed with DTI will also be studied to determine if axonal injury resulting from TBI was associated with greater amyloid accumulation, or whether regions of brain with axonal damage have less amyloid accumulation due to disconnection and reduced brain activity.

Primary Analyses: Comparing Groups on Baseline Level (Hypothesis sets 1 & 3):

Primary outcomes for these analyses include uptake on Florbetapir scans, CSF amyloid beta, CSF tau and Ptau, volumes of the hippocampus, entorhinal cortex, and parietal/temporal cortices, DTI summary measures (in the third set of hypotheses) and measures of cognitive function, including delayed episodic memory.

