The analyses will begin with: 1) numerical and graphical summaries of the measures within each group to assess the underlying distribution and detect outliers or questionable values which will be flagged and checked with the sites for accuracy. 2) Analysis of variance (ANOVA) for a simple unadjusted comparison between the groups. If the global F-test for group difference is significant, there will be a follow-up with post-hoc pairwise tests, specifically between the TBI or PTSD groups and the Veteran control group, adjusted for multiple comparisons using the Bonferroni or Tukey's Honestly Significant Difference (HSD) approach. 3) linear regression models that include group as an independent variable to adjust for potential confounders including age, gender, APOe4 genotype, and alcohol dependence. Model assumptions will be assessed through graphical and numerical approaches and transformations or non-linear models will be used if suggested by the diagnostics. Hypotheses will be supported if the TBI and PTSD groups show significantly higher levels of uptake on amyloid PET scans and CSF tau or Ptau than the Veteran controls and significantly lower levels of CSF amyloid beta, MRI volumes, and cognitive function than the Veteran controls.

Primary Analyses: Comparing Groups on Annual Change (Hypothesis sets 1 & 3):

Primary outcomes for these analyses include annual change in volumes of the hippocampus, entorhinal cortex, and parietal/temporal cortices and annual change in cognitive function such as delayed recall. There will be two assessments for each person, approximately one year apart. Therefore, for each participant as a measure of annual change, there will be a construction of difference scores between the measures obtained at the follow-up visit and the baseline visit. The scores will be divided by the time between the assessments to account for variability in timing of the follow-up assessments between participants. Analyses will be similar to those described above for comparing groups on the baseline level except that the final linear regression models will also be adjusted for baseline level of the outcome measure. Hypotheses will be supported if the TBI and PTSD groups show significantly faster rates of atrophy and cognitive decline than the Veteran controls.

TBI or PTSD associated with reduction in cognitive reserve (Hypothesis set two):

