As described earlier, exploratory analyses will be performed to examine other questions; although, after correction for multiple comparisons, power will be low requiring future replication. Nevertheless, there will be a comparison of the patterns (using voxel based methods) of amyloid deposition (from amyloid PET) and brain atrophy between TBI, PTSD, and control subjects, and with similar patterns from non Veteran subjects in ADNI. The results of these studies may provide insight into the question of whether or not TBI and PTSD alter the pattern of amyloid distribution or brain atrophy. Furthermore, the relationships between amyloid deposition, atrophy, and cognitive function may provide insight into the question of whether TBI or PTSD is associated with reduced cognitive reserve. Further exploratory analyses will assess the relationship between cortical areas with amyloid plaque (from amyloid PET) and underlying white matter integrity as assessed with DTI to determine if axonal injury resulting from TBI was associated with greater amyloid accumulation, or whether regions of the brain with axonal damage have less amyloid accumulation due to disconnection and reduced brain activity. Linear regression methods, described above, will be used to assess the association between regional measures of amyloid accumulation and axonal damage.

Power Analysis:

Power analyses are presented for each class of primary hypotheses assuming a two-sided test and were calculated using nQuery. For comparison of the TBI or PTSD group to the Veteran controls, assuming alpha = 0.025 to account for multiple comparisons and 65 individuals per group at baseline and 61 per group for longitudinal measures, there will be an 80% power to detect a difference as small as 0.55 standard deviations in level and as small as 0.56 standard deviations in rate of atrophy or cognitive decline. For example, using means and standard deviations from measures in the normal controls within ADNI-1, this difference would translate to at least a 6.7% lower hippocampal volume, and at least a 14.7% lower CSF amyloid beta. Because there is little change in the ADNI normals, differences in change will be much more difficult to detect. However, these data will provide initial estimates of how much change is experienced in the TBI and PTSD groups which will help in planning larger scale

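### The H1 support rule requires all outcomes in both exposure groups, but the stated alpha of 0.025 and 80% power describe one outcome and one contrast

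*Protocol*

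**What the plan says.** All of this is in Protocol Section 24.

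- **Outcomes.** The baseline-level subsection states: "Primary outcomes for these analyses include uptake on Florbetapir scans, CSF amyloid beta, CSF tau and Ptau, volumes of the hippocampus". It goes on to entorhinal cortex, parietal/temporal cortices and cognitive function. DTI summaries are also listed but belong to the third hypothesis. The annual-change subsection adds change in the three regional volumes and in cognition. None is ranked above the others.
- **Adjustment.** After a significant global F-test, the pairwise group tests are adjusted by Bonferroni or Tukey's HSD. This works within one outcome. Correction beyond the group contrasts is mentioned only for the exploratory analyses.
- **Support rule, baseline.** "Hypotheses will be supported if the TBI and PTSD groups show significantly higher levels of uptake on amyloid PET scans and CSF tau or Ptau", relative to controls, together with significantly lower amyloid beta, MRI volumes and cognitive function. The only 'or' is between tau and Ptau. The annual-change rule likewise joins atrophy with cognitive decline, and TBI with PTSD.
- **Power.** The calculations are described as "assuming a two-sided test and were calculated using nQuery", "assuming alpha = 0.025 to account for multiple comparisons", with "65 individuals per group at baseline and 61 per group for longitudinal measures". The result is that "there will be an 80% power to detect a difference as small as 0.55 standard deviations in level and as small as 0.56" in rate of change.

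**The concern.** The support rule and the power statement describe different tests. An alpha of 0.025 equals 0.05/2, which matches the two contrasts with controls on a single outcome, although the protocol does not state the divisor. The rule spans about a dozen outcomes and two exposure groups.

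Two consequences pull in opposite directions. If the rule is applied as worded, the study will probably fail to support H1 even when every effect has the planned size. If it is applied loosely, so that any one significant outcome counts, increased evidence for AD could be claimed by chance far more often than 5% of the time. The protocol does not say which reading governs. It also says that the results will lead to the design and powering of a prevention trial, so what counts as support matters.

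**Working it through.** **Inputs from the protocol.** Two-sided alpha 0.025; 65 per group at baseline and 61 for change; detectable differences 0.55 and 0.56 SD.

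**Outcome count for H1.** Baseline: florbetapir, amyloid beta, tau, Ptau, hippocampus, entorhinal cortex, parietal/temporal cortices and cognition = 8. Change: three volumes and cognition = 4. The total is 12 outcomes, or 12 × 2 = 24 tests. Cognition is counted once although the battery is large, and counting parietal and temporal separately would give 14 outcomes.

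**Assumption.** The protocol gives no correlation between outcomes. An equal correlation r of 0 to 0.5 is assumed.

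**Step 1: reproduce the stated power.** For two means, the noncentrality is d × √(n/2).
- Level: 0.55 × √(65/2) = 3.14 on 128 df; power 80.6% by noncentral t (81.4% by the normal approximation).
- Change: 0.56 × √(61/2) = 3.09 on 120 df; power 79.4% (80.3% normal).

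Both agree with the stated 80%. At alpha 0.05 the figures would be 87.5% and 86.6%, so 0.025 is the level used. Under the null, the chance that either contrast is significant on a single outcome is 4.6%.

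**Step 2: one outcome, both exposure groups required.** The two contrasts share the control group and so correlate 0.5. Simulated power is about 71%.

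**Step 3: the baseline rule as worded.** Six outcomes must each be significant, plus tau or Ptau. At r = 0, for one exposure group (normal approximation):

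0.814^6 × [1 − (1 − 0.814)^2] = 0.291 × 0.965 = 0.28

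The other entries are from 200,000 simulated trials with |z| > 2.241 and every true effect at 0.55 SD:

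| r | one exposure group | both groups |
|---|---|---|
| 0 | 28% | 12% |
| 0.3 | 41-42% | 24% |
| 0.5 | 50% | 32% |

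**Step 4: any one outcome suffices (12 outcomes, 2 contrasts, no true effect).** At r = 0, counting either direction: 1 − (1 − 0.046)^12 ≈ 0.43. Simulation gives:

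| Counting | r = 0 | r = 0.3 | r = 0.5 |
|---|---|---|---|
| either direction | 43-44% | 38% | 31% |
| hypothesised direction only | 25% | 20% | 16% |
| hypothesised direction, after the F-test gate | just under 20% | 16% | 13% |

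The rule names a direction for each outcome, so the second and third rows are the relevant ones. The second applies to the adjusted regression step, for which no gate is stated.

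**Step 5: cost of control across outcomes.** Full Bonferroni uses 0.05/24 = 0.00208, which is also 0.025/12, the first Holm step within one exposure group. Power at 0.55 SD with 65 per group is then 50%, and the detectable difference is 0.70 SD.

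**The case against.** The strongest defence is that each outcome and contrast is its own hypothesis. Section 24 numbers the manifestations of H1 and calls them hypotheses in the plural, the support sentence also uses the plural, and power is given for each class of hypotheses and for the TBI *or* PTSD group. On that reading 0.025 and 80% are both correct. This stands. A reader might infer that the stated figures hold under no reading at all, and the documents do not support that. Nor does the all-outcomes reading inflate type I error: it is conservative, and only power falls short.

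The largest any-outcome error rate (31-44%) counts results in either direction, while the protocol's rule is directional. This also stands, and the lower figures are the ones to use. If the one outcome had to be significant in both TBI and PTSD, the error would be only about 2%.

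Control across outcomes may sit in an SAP that is not shown, so its absence is not in itself the point. What remains is that this document contains a conjunctive rule and a single-test power figure that do not match.

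Three further inferences should be resisted.
- **Repeated looks.** The Synopsis says: "Analysis of the data to test the hypotheses as stated, including the exploratory analyses, will begin after the first 12 months or so". A reader might infer inflation from interim testing. No number of looks, re-testing of the same hypothesis or stopping decision is stated, so no figure can be attached.
- **Hippocampus in PTSD.** H1 counts a smaller hippocampus as AD evidence, while Section 5, Third Hypothesis, says: "Previous findings of reduced hippocampal volume in PTSD compared to controls will also be replicated". That overlap affects how a positive result is interpreted. It is not an alpha error, and the Synopsis lists hippocampal atrophy accounting for amyloid as an outcome.
- **Florbetapir as the sole confirmatory outcome.** The protocol lists it first but does not rank it above the rest. Elevating it would narrow H1 and is a matter of preference.

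**Conclusion.** The point holds as a mismatch within Section 24, and it should be fixed. The stated alpha and power are arithmetically right for one outcome and one contrast. They do not describe the support rule as worded, whose power at the planned effect size is 28-50% for one exposure group and 12-32% for both. Requiring even a single outcome in both groups gives about 71%. If any outcome may support H1, the false-positive chance in the hypothesised direction is about 16-25%, or 13% to just under 20% with the F-test gate.

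These figures rest on equally correlated outcomes (r from 0 to 0.5), every effect exactly at the planned size, and cognition counted once. At r = 0.7 the power of the worded rule rises to 58% and 42%, still well below 80%. This is a natural history study with no treatment decision attached, which limits the consequence but does not settle what may be concluded about H1.

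**What to change.** 1. In Section 24, Power Analysis, state that 80% is the unadjusted power per outcome and per contrast, and that it is not the power of the support rule.
2. In the baseline-level subsection, replace the conjunctive sentence with a rule that judges TBI and PTSD separately, each at 0.025, using Holm or a prespecified fixed order across the H1 outcomes. Increased evidence for AD is then claimed only for the outcomes that survive.
3. Bring the matching sentence in the annual-change subsection into line.

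This needs no extra participants or procedures. The cost is power per outcome: about 50% at 0.55 SD in the worst case (full Bonferroni over 24 tests). Holm can do no worse than that, and a fixed order keeps the stated power for the outcome placed first but makes later outcomes depend on earlier ones. Holding 80% at 0.55 SD under the full Bonferroni would take about 104 per group, slightly above the top of the protocol's 65-100 range.

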TBI and PTSD are common problems resulting from military service. Thus far, there have been no prospective studies using imaging and biomarkers, which directly measure changes in the brain and AD pathology to study the effects of TBI and PTSD. This proposed study will provide novel data to test these hypotheses. The results will have major implications for identifying, subjects at increased risk for AD, a possible need for early detection of AD in military Veterans with histories of TBI and PTSD, and a possible need to employ prevention and treatment measures to avoid accelerated development of AD in US military Veterans. This study is a first step toward a larger, more comprehensive study of dementia risk factors in Veterans. The results will lead to a design and statistical powering of a prevention trial. Therefore, this project could be the first step toward the prevention of AD in Veterans, and in the general population.

2. Background: AD, TBI, & PTSD

Alzheimer's disease (AD) is characterized by brain pathology consisting of extracellular plaques containing amyloid β (A β), tangles of phosphorylated tau protein inside neurons, synapse loss (which begins in the entorhinal cortex and hippocampus in the medial temporal lobe) and neuronal loss, leading to dementia. It is generally recognized that age and family history are the major risk factors for the development of AD. Evidence also exists that several factors including occupation, education, and intellectual/social activity affect cognitive decline and incidence of AD, leading to the concept of "cognitive reserve" [1]. Although acetylcholine-esterase inhibitors and memantine are approved for treatment of AD, these produce modest symptomatic improvement, but do not slow the progression of AD. Currently a large number of treatment trials are underway. Most use immunotherapy (vaccines or monoclonal antibodies) or secretase inhibitors (to reduce synthesis of A β), but none have been successful. Most treatment trials are conducted using patients with dementia due to AD, although an increasing number are enrolling subjects with mild cognitive impairment (MCI) who have evidence of AD pathology (using imaging/biomarkers). A long-term goal of the field will be to prevent the development of cognitive impairment or dementia by treatment of normal subjects. Previous attempts at prevention trials with Ginkgo Biloba [2] or non-steroidal anti-inflammatory drugs [3,4] have failed.

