Primary analyses involve comparing groups on baseline levels of CSF, Neuroimaging (MRI and amyloid PET), and cognitive measures associated with AD pathology and annual change in MRI and cognitive measures to assess whether PTSD or TBI is associated with increased evidence for AD compared to Veteran controls. Further analyses will focus on within-group correlations to assess a doseresponse association between outcomes and severity of PTSD or TBI and whether TBI or PTSD reduces cognitive reserve. Additional exploratory analyses will also be conducted. The specific analytic methods for hypothesis testing are listed below followed by an assessment of power.

The primary hypotheses to be tested (all data analyses will be covaried for age, gender, and APOe4 genotype) are that Veterans without MCI (or dementia, with a history of moderate to severe TBI during military service, as well as Veterans with ongoing PTSD, have increased evidence for AD, when compared with Veteran controls (without TBI or PTSD) manifested as: 1) greater uptake on Florbetapir amyloid PET scans; 2) lower CSF amyloid beta levels; 3) increased CSF tau/P tau levels; 4) brain atrophy in hippocampus, entorhinal cortex, and parietal/temporal cortices; and 5) greater rates of brain atrophy in hippocampus, entorhinal cortex and parietal/temporal cortices; 6) reduced cognitive function, especially delayed recall.

The second major hypotheses to be tested is that TBI and/or PTSD reduce brain reserve causing greater cognitive impairment after accounting for age, brain amyloid load or hippocampal volume. Greater cognitive impairments at a given level of brain A\beta or brain volume in the TBI or PTSD group compared with controls would support the hypothesis of reduced cognitive reserve.

The third hypothesis will be that TBI, when compared to controls, is associated with changes detected with DTI in brain regions previously reported to be associated with TBI [37-39].

Finally, the hypothesis that there will be significant correlations between severity of TBI (determined from medical records) and severity of PTSD (CAPS score) on the above-listed outcomes in the TBI and PTSD groups respectively will be tested.

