The main outcomes for these analyses will be level and annual change in cognitive function, particularly memory while the predictors of interest are group, baseline hippocampal volume, and uptake from the amyloid PET scans. Linear regression methods similar to those described above will be used. Of particular interest for these analyses are the interactions between group and the imaging predictors. Power will be limited for these analyses, so results will mainly serve as support for future studies of PTSD, TBI, and cognitive reserve. However, significant interactions suggesting worse cognitive function

in the TBI or PTSD groups relative to Veteran controls at a given level of MRI, or amyloid imaging measures would support the hypotheses.

Within-group correlations to assess dose-response:

Outcomes for these analyses will be the same as those used for hypothesis sets one, two, and three. Interest lies in assessing whether the baseline levels or rates of atrophy or cognitive decline are associated with severity of TBI or PTSD. Analyses will be performed within each of those groups separately. Severity of TBI or PTSD will be the predictor of interest. Simple linear regression models that include severity of TBI or PTSD as the independent variable will be used. Multiple regression models to adjust for potential confounders including age, gender, and APOe4 genotype and alcohol dependence will be used next. As stated above for the primary analyses, model assumptions will be assessed and transformations or non-linear models will be used if suggested by the diagnostics. Secondary hypotheses will be supported if increased severity of TBI or PTSD is significantly associated with lower levels of CSF amyloid beta, MRI volumes, and cognitive function, higher levels of CSF tau or Ptau, and increased rates of brain atrophy and cognitive decline.

Exploratory Analyses:

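### The cognitive-reserve analysis holds amyloid uptake and hippocampal volume constant but not CSF tau or P-tau, so a deficit read as reduced reserve could partly reflect extra tau pathology

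*Protocol*

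**What the plan says.** Protocol section 24, on hypothesis set two, takes level and annual change in cognition as outcomes and states that "the predictors of interest are group, baseline hippocampal volume, and uptake from the amyloid PET scans". It gives most weight to interactions between group and the imaging predictors. Support would come from "significant interactions suggesting worse cognitive function" among the exposed than among controls when MRI or amyloid imaging is held equal. The same paragraph says that power is limited and that the results will mainly serve future studies.

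The hypothesis itself is worded more broadly. The opening of section 24 describes TBI or PTSD as "causing greater cognitive impairment after accounting for age, brain amyloid load or hippocampal volume". Section 5 (Second Hypothesis) gives the reading rule, under which the following is to count as evidence of reduced cognitive reserve: "Greater cognitive impairments at a given level of brain Aβ or brain volume in the TBI or PTSD group compared with controls". Section 5 also lists education and the pre-war qualifying examination score as things to account for. The regression methods carried over from the primary analyses adjust for confounders that include age, gender, APOE4 and alcohol dependence. Tau is named in none of these places.

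Elsewhere the protocol treats tau as part of the disease. Section 2 describes AD pathology as including "tangles of phosphorylated tau protein inside neurons". The synopsis (Outcome Measures, item 3) lists amyloid PET, CSF Aβ and tau, and medial temporal lobe atrophy as the measures of brain AD pathology. The primary hypothesis in section 5 predicts "Increased CSF tau/P tau levels" in both exposed groups. CSF is collected at baseline, and section 24 makes tau and P-tau primary baseline outcomes.

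**The concern.** A reserve claim says that cognition is worse than the pathology explains. The model accounts for two of the protocol's markers of pathology, amyloid and atrophy, and leaves out a third that the protocol itself expects to differ between the groups. If tau lowers cognition, and the exposed groups carry more of it than their amyloid and hippocampal volume predict, the group coefficient picks up that excess. Under the reading rule in section 5, an AD-burden effect (hypothesis 1) could then be counted as support for an effect beyond burden (hypothesis 2). The results are meant to inform future studies of reserve, so a misattributed signal could be carried into them.

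**Working it through.** **The plan's own figure.** The protocol gives no figure for the reserve test. The nearest is the detectable group difference in section 24 (Power Analysis): 0.55 SD in level with 65 per group and 0.56 SD in change with 61 per group, at 80% power and two-sided alpha 0.025. With power = Φ(d·√(n/2) − 2.241):
- n = 65, d = 0.55: Φ(3.135 − 2.241) = Φ(0.894) = 81.4% (80.6% with the noncentral t).
- n = 61, d = 0.56: Φ(3.093 − 2.241) = Φ(0.851) = 80.3% (79.4% with the noncentral t).

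Both figures reproduce.

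**Assumed inputs for the bias (none is in the documents).**
- Tau is higher by d = 0.30 to 0.55 SD in the exposed group. The upper end is the protocol's detectable difference.
- Tau lowers cognition by b = 0.3 to 0.5 SD per SD.
- Within-group correlations are 0.3 for tau with amyloid, −0.3 for tau with hippocampal volume and −0.2 for amyloid with hippocampal volume.
- There is no reserve effect.

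**Closed form.** Regressing tau on amyloid and hippocampal volume within group gives coefficients c_A and c_H that solve c_A − 0.2·c_H = 0.3 and −0.2·c_A + c_H = −0.3. Hence c_A = 0.25 and c_H = −0.25. With tau left out, the bias in the group coefficient is −b × (tau shift − 0.25 × amyloid shift + 0.25 × hippocampal shift).

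1. *Only tau shifts:* bias = −b·d. This runs from −0.3 × 0.30 = −0.09 SD to −0.5 × 0.55 = −0.275 SD.
2. *Amyloid rises and hippocampal volume falls by the same d, as hypothesis 1 also predicts:* bias = −b·d × (1 − 0.25 − 0.25) = −0.5·b·d. This runs from −0.045 SD to −0.1375 SD. If the amyloid–hippocampus correlation is −0.3, both coefficients are 0.3/1.3 = 0.231 in size, the factor is 1 − 0.462 = 0.538, and the upper end is about −0.15 SD.
3. *Only amyloid is held constant, which the word or in the reading rule allows, and all markers shift:* the part due to tau is −b·d × (1 − 0.3) = −0.7·b·d, or −0.063 to −0.19 SD.

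**Error rates by simulation** (65 per group, 4,000 runs per setting, two-sided alpha 0.025, amyloid and hippocampal effects of 0.2 each). False support is a significant deficit in the predicted direction, nominally 1.25%.

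| Scenario | Spurious group deficit (SD) | False support without tau | With tau added |
|---|---|---|---|
| Only tau shifts | 0.09 to 0.27 | 4.7% to 27% | 1.3% to 1.4% |
| All three markers shift | 0.04 to 0.13 | 2.2% to 7.2% | 1.3% to 1.5% |

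**The interaction named in section 24.** In the same settings the group-by-amyloid term rejects in 2.2% to 2.7% of runs (nominal 2.5%, two-sided), so a shift in level does not inflate it. It is inflated if tau rises more steeply with amyloid in the exposed group. With an extra slope of 0.5 SD per SD and d = 0.55, it rejects in 8.6% of runs for b = 0.3 and 14.2% for b = 0.4. Adding tau brings these to 1.9% and 2.4%.

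**The case against.** The strongest reply is that the protocol defines its own contrast, cognition relative to amyloid or brain volume, and that section 24 tests it. Equality on all pathology is a stricter construct. This stands in part: there is no internal contradiction, only a conclusion worded more widely than the adjustment supports. The same logic might seem to require white-matter injury on DTI, which hypothesis 3 expects to differ in TBI. But the protocol's own list of AD pathology measures includes tau and not DTI, and that is a reason to stop at tau.

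A reader might infer that hypothesis 1 invalidates the formal interaction test. It does not. Hypothesis 1 concerns levels of tau, a level shift leaves the interaction unbiased, and the protocol does not predict a group difference in the tau–amyloid slope. A reader might also take the case where only tau shifts as the expected one. Hypothesis 1 equally predicts higher amyloid and smaller hippocampi; both are in the model and absorb about half of the bias under these assumptions.

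A third tempting inference is that extra tau would be declared reduced reserve, and that the trial cannot separate its first two hypotheses. That goes too far. Tau and P-tau are compared directly between groups as primary outcomes, so a tau difference would be visible beside any reserve result, and section 24 already calls the reserve analyses limited in power and mainly supportive.

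Finally, the covariate list is open, and a statistical analysis plan could add tau. That is fair for the model. The reading rule, however, is fixed in the protocol and takes no account of tau.

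**Conclusion.** The point holds as a limit on interpretation. Section 24's named predictors and the reading rule in sections 5 and 24 leave out a marker that the protocol counts as AD pathology and expects to be higher in TBI and PTSD. A deficit at a given amyloid level or brain volume could therefore partly reflect tau. On the assumed inputs, the spurious group deficit is about 0.05 to 0.15 SD when amyloid and hippocampal volume move with tau, and up to about 0.28 SD when only tau moves. The latter is half of the 0.55 SD that the study is powered to detect. The direction follows from the protocol's own hypotheses if tau worsens cognition and the groups still differ in tau at equal amyloid and volume; hypothesis 1 makes that residual difference plausible but does not strictly imply it. The size rests wholly on assumed tau–cognition, tau–amyloid and tau–volume relations. The interaction test is at risk only if those relations differ by group.

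**What to change.** In section 24 (hypothesis set two), also fit each model with baseline CSF tau or P-tau as a further pathology predictor beside amyloid uptake and hippocampal volume. Include its interaction with group where the group-by-amyloid interaction is tested. Report results with and without tau. In sections 5 and 24, state that a finding which does not persist with tau in the model will be described as worse cognition relative to amyloid and hippocampal volume, not as reduced reserve.

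No new data are needed. The cost is one or two degrees of freedom in an analysis already short of power, and the loss of subjects without a usable CSF sample. To keep that loss from being mistaken for an effect of tau, the model without tau should also be shown in the subjects who have CSF.
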